between the intersection of two lines: the first line drawn from the tragus of the ear to the spinous process of C7 vertebrae and the second line drawn horizontally through C7 spinous process (Kim et al. 2016). A second researcher directly observed the PI perform each CVA assessment, as well as provided verbal agreement with the accuracy of angle measurement. For each participant, the CVA was derived by taking the mean of two CVA measurements that were assessed on the captured photographs (Kim et al. 2016).

Inclusion criteria included completion of informed consent, craniovertebral angle  $\leq 53$  degrees (Lee et al. 2017) and self-rating of Transtheoretical Model stage of change stage  $\geq 3/5$  on a questionnaire to indicate their readiness to comply with an assigned exercise prescription or postural guidelines (Kuroda et al. 2012). Exclusion criteria consisted of any musculoskeletal injury to the head, shoulders, or spine within the last six months; diagnosis of pathology related to the cervical spine, thoracic spine, or upper extremities; or non-clearance for physical activity based on results of the PAR-Q+ questionnaire. A total of 79 participants met inclusion criteria and were included in the study.

Randomization of participant group assignments was completed by the PI using a block randomization generator on a website (<http://www.randomization.com>). Utilizing a sequence created by the block randomizer, the PI placed participants who met inclusion criteria into one of four groups: (PE; n = 20), self-myofascial release + stretching (SMRS; n = 20), self-myofascial release + stretching + strengthening (SMRSS; n = 19), and control group (CG; n = 20). A hard-copy of the sequence generator report was kept concealed in a manila folder and was only opened by the PI during group delegation. Participants and researchers were not blinded to group assignment.

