### **Statistical Analysis**

Data were analyzed using IBM SPSS version 28 for Windows (SPSS Inc., Chicago, IL, USA) and reported with mean and standard deviation. Descriptive participant characteristics by group were analyzed with a one-way ANOVA. Paired samples *t*-tests were used to assess within-group differences in means between pre- and post-intervention CVA measures. Between-group comparisons of post-intervention mean CVA change were analyzed with a one-way ANOVA. Levene's test was utilized to assess equality of error variance. Gabriel's test was selected for post-hoc comparisons. The significance level was set at  $p < 0.05$ .

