## **Results**

The trial was completed by 72 participants (51 females, 21 males) with a mean age: 20.17 (SD:  $\pm 2.25$  years); mean height: 167.34 (SD:  $\pm 8.25$  cm); and mean weight: 70.31 (SD:  $\pm 14.61$  kg). All participants reported SOC self-rating  $\geq 3/5$ . Pre-intervention analysis revealed no significant difference ( $p > 0.05$ ) in participant age or anthropometric characteristics between groups. No significant between-group differences ( $p > 0.05$ ) in baseline CVA were present. Within-group comparisons of pre- vs post-intervention CVA outcomes revealed a significantly ( $p < 0.05$ ) greater post-intervention CVA in the PE, SMRS, SMRSS, and CG. Post-hoc comparisons indicated post-intervention mean CVA change in the SMRS group: 3.8 (SD:  $\pm 3.3$  deg.); and the SMRSS group: 4.4 (SD:  $\pm 3.1$  deg.); was significantly greater ( $p < 0.01$ ) than the CG: 0.8 (SD:  $\pm 1.7$  deg.). All participants in the SMRS and SMRSS groups reported intervention adherence as moderately consistent (50-75% sessions performed) or higher on both the mid- and post-study questionnaire. 91% of the PE group reported intervention adherence as moderately consistent (50-75% adherence to guidelines) or higher on the mid-study questionnaire. 96% of the PE group reported intervention adherence as moderately consistent or higher on the post-study questionnaire.

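### The ANOVA and Gabriel's test use one pooled variance although the printed change SDs run from 1.7 to 3.3, so the error term may not fit individual contrasts, notably postural education versus control

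*Combined protocol and SAP*

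**What the plan says.** The Statistical Analysis section compares CVA change between the four groups by one-way ANOVA. On the variance assumption and the pairwise tests it says only: "Levene's test was utilized to assess equality of error variance. Gabriel's test was selected for post-hoc comparisons". It does not say what happens if Levene's test rejects.

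The Results give no Levene result. The sentence beginning "Post-hoc comparisons indicated post-intervention mean CVA change in the SMRS group: 3.8" reports change as mean (SD): SMRS 3.8 (3.3), SMRSS 4.4 (3.1) and control (CG) 0.8 (1.7) degrees, with p < 0.01 for each exercise arm against CG. For PE there is only a within-group statement, that all arms had "greater post-intervention CVA in the PE, SMRS, SMRSS, and CG". The PE mean change, its SD and the PE–CG comparison are not given.

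Arm sizes are known only at randomisation: the Study Protocol section places participants "into one of four groups: (PE; n = 20"), SMRS 20, and "strengthening (SMRSS; n = 19), and control group (CG; n = 20"). The Results say "The trial was completed by 72 participants", without a split by arm.

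**The concern.** One-way ANOVA and Gabriel's test both estimate one error variance from all four arms and use it for every pair. If the exercise arms vary more than the control arm, that estimate is a compromise. It is too large for a pair of less variable arms and too small for the pair of more variable ones.

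PE versus CG is the trial's only test of education against no intervention. If the PE SD is near or below those of the exercise arms, the pooled error makes a PE effect harder to detect, while SMRSS versus SMRS is tested too leniently. An acceptable overall error rate would not reveal either distortion.

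**Working it through.** **Inputs.** From the Results: the means and SDs above and 72 completers. From the Study Protocol section: 20/20/19/20 randomised, so 79 − 72 = 7 lost and error df = 72 − 4 = 68. Assumed because not printed: 18 completers per arm; PE SD of 1.7, 2.5, 3.3 or 4.0; normal data; two-sided tests. Slash-separated results follow that order of PE SDs.

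**1. Are the spreads unequal?** The variance ratio SMRS to CG is (3.3/1.7)² = 3.77. Treated as the largest-to-smallest ratio among four arms, with the PE SD between 1.7 and 3.3, p is about 0.043 at 18 per arm (0.027–0.066 from rounding of the SDs). This is suggestive only.

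**2. The printed p-values.** Pooled SD = √[(3.3² + 3.1² + 1.7² + SD_PE²)/4] = √[(23.39 + SD_PE²)/4] = 2.56/2.72/2.93/3.14. With equal arms the pooled SE is this times √(2/18), that is, divided by 3: 0.85/0.91/0.98/1.05. Gabriel's critical values (studentized maximum modulus, 6 comparisons, 68 df) are 2.706 at 0.05 and 3.272 at 0.01. For SMRS–CG, (3.8 − 0.8)/SE = 3.51/3.31/3.07/2.87, giving p = 0.0048/0.0090/0.018/0.032. So p < 0.01 is reachable, but at 18 per arm only if the PE SD is at most 2.6. Rounding makes that bound 2.0–3.1. Uneven dropout makes it 2.2–3.4, or up to 3.99 with rounding as well.

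**3. Pooled SE over the contrast's own SE.**
- PE–CG: own SE = √[(SD_PE² + 1.7²)/18] = 0.57/0.71/0.87/1.02; ratio 1.51/1.27/1.12/1.02.
- SMRSS–SMRS: own SE = √[(3.3² + 3.1²)/18] = 1.07; ratio 0.80/0.85/0.91/0.98.

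**4. Observed PE–CG difference needed for adjusted p < 0.05.** Gabriel: 2.706 × SE = 2.31/2.46/2.64/2.83 degrees. Games-Howell: 1.53/1.94/2.40/2.84 degrees.

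**5. Power for PE–CG** (simulation, 18 per arm, good to about one point):

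| True difference | Gabriel | Games-Howell |
|---|---|---|
| 2 degrees | 31/28/24/22% | 79/54/34/24% |
| 3 degrees | 87/77/66/57% | 99/92/75/57% |
| 4 degrees | 100/98/94/87% | 100/100/96/86% |

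At 2 degrees, 3.6/3.0/2.5/2.2 points of the gap come from Gabriel's stricter critical value rather than from pooling; a pooled Tukey test gives 35/31/27/24%. At the PE SD bound of 2.6 the 2-degree comparison is 27% against 50%.

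**6. Uneven dropout.** Over all 100 splits of the seven losses that leave at least 17 in CG, the 2-degree change in power from using Games-Howell is +41 to +51, +18 to +29, +1 to +14 and −6 to +5 points.

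**7. Error rates under no effect.** Familywise error at 18 per arm is 4.9–5.4% for Gabriel and 5.0–5.1% for Games-Howell; over the splits, 4.1–7.8% and 4.6–5.4%. By contrast, for PE SD 1.7–3.3 Gabriel rejects PE–CG in about 0.01–0.4% of trials and SMRSS–SMRS in about 1.6–3.5%, around a nominal per-pair rate of about 0.9%.

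**8. Printed contrasts under Games-Howell.**
- SMRS–CG: SE √[(3.3² + 1.7²)/18] = 0.875, t = 3.43, df 25.4, p = 0.0105 (0.007–0.016 from rounding).
- SMRSS–CG: SE 0.833, t = 4.32, df 26.4, p = 0.0011 (0.0006–0.0018).
- SMRSS–SMRS: p = 0.94.

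Over uneven splits the first two run 0.006–0.036 and 0.0007–0.0102.

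**9. Limits on the assumed arm sizes.** CG change of 0.8 (SD 1.7) gives a paired t of 0.8/(1.7/√18) = 2.00, p = 0.062, at n = 18, and p = 0.049 at n = 20. The Results report p < 0.05, so 18 fits only with favourable rounding; with such rounding CG must be at least 17. The PE count is also unclear. The Results say "91% of the PE group reported intervention adherence as moderately consistent" mid-study and "96% of the PE group reported intervention adherence as moderately consistent or higher on the post-study questionnaire". No count out of 20 or fewer rounds to 96%; the first is 22/23, and 23 is the only denominator up to 40 that also gives 91% (21/23). With 23 PE completers and 16/16/17 elsewhere, 2-degree power is 41/33/26/21% for Gabriel and 83/63/43/30% for Games-Howell.

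**The case against.** The strongest case against is that nothing printed changes. Both reported contrasts stay below 0.05, SMRSS–SMRS is null under either method, and familywise error is about right with equal arms. The harm is confined to a contrast whose result is not shown, and its size depends on an unprinted SD: the 2-degree gain runs from 48 points to almost none, and can be negative. The 2-degree effect is illustrative, since the documents give no target difference. All of this stands and limits the weight of the point.

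Unequal variance is also unproven, and Levene's test may have been run and not rejected. That stands too, but it would not establish equality: with SDs like these and a PE SD of 1.7–3.3, Levene's test rejects in only about 55–79% of trials at 18 per arm.

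A further objection is that switching method after seeing the SDs is data-driven. This has force for reporting, so the Gabriel results should stay visible. It does not remove the case for Welch methods, which rests on their small cost under equal variances as well as on these SDs.

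Finally, the adherence percentages and missing completer counts are reporting gaps, not results of pooling. That is fair; they matter here only because arm size enters every standard error.

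**Conclusion.** The concern holds and should be acted on, with medium confidence. The plan uses one pooled variance throughout, attaches no consequence to its variance check, and is followed by SDs that suggest the assumption fails. At 18 per arm, the PE–CG standard error is overstated by about 51% if the PE SD is 1.7, 12% if it is 3.3 and 2% if it is 4.0. The SMRSS–SMRS error is understated by 20% to 2% over the same range.

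If the printed p < 0.01 for SMRS–CG is Gabriel's, the PE SD probably lies where the loss of PE–CG power is appreciable. Uneven arms and rounding together leave room for no loss at all. No printed conclusion at 0.05 is overturned. The Games-Howell p for SMRS–CG cannot be distinguished from 0.01 with the rounded figures available.

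**What to change.** Make Welch's ANOVA with Games-Howell comparisons the between-group analysis of CVA change, not conditional on Levene's test. Keep the Gabriel results beside it, labelled as the analysis the document states. Report all six contrasts, including PE versus CG, with simultaneous 95% confidence intervals and exact adjusted p-values. Let the exact SMRS–CG value replace the p < 0.01 label, with no claim that it crosses 0.01. Print the PE mean and SD of change and the completers per arm, reconcile the latter with the 91% and 96% adherence denominators, and give Levene's result as description only.

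The cost is a change of wording and a re-run of existing data, with fewer degrees of freedom per contrast. If variances are in fact equal (common SD 2.7, 18 per arm, 2-degree difference), power is 32.8% with Games-Howell against 32.1% with Gabriel and 34.6% with pooled Tukey. The worst case is a PE arm that is both the most variable (SD 4.0) and the most depleted: Games-Howell then gives up to about 6 points less PE–CG power, because the pooled error is too small there.

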## **Results**

The trial was completed by 72 participants (51 females, 21 males) with a mean age: 20.17 (SD:  $\pm 2.25$  years); mean height: 167.34 (SD:  $\pm 8.25$  cm); and mean weight: 70.31 (SD:  $\pm 14.61$  kg). All participants reported SOC self-rating  $\geq 3/5$ . Pre-intervention analysis revealed no significant difference ( $p > 0.05$ ) in participant age or anthropometric characteristics between groups. No significant between-group differences ( $p > 0.05$ ) in baseline CVA were present. Within-group comparisons of pre- vs post-intervention CVA outcomes revealed a significantly ( $p < 0.05$ ) greater post-intervention CVA in the PE, SMRS, SMRSS, and CG. Post-hoc comparisons indicated post-intervention mean CVA change in the SMRS group: 3.8 (SD:  $\pm 3.3$  deg.); and the SMRSS group: 4.4 (SD:  $\pm 3.1$  deg.); was significantly greater ( $p < 0.01$ ) than the CG: 0.8 (SD:  $\pm 1.7$  deg.). All participants in the SMRS and SMRSS groups reported intervention adherence as moderately consistent (50-75% sessions performed) or higher on both the mid- and post-study questionnaire. 91% of the PE group reported intervention adherence as moderately consistent (50-75% adherence to guidelines) or higher on the mid-study questionnaire. 96% of the PE group reported intervention adherence as moderately consistent or higher on the post-study questionnaire.

